4.2 Analysis methods

4.2.1 Disposition of subjects

The number and percentage of subjects who were enrolled to the study, randomized, randomized and received treatment, randomized and did not receive treatment, completed treatment, discontinued prematurely from treatment, completed the study, withdrew from the study, and reasons for withdrawal from the study will be summarized by treatment group and overall for all subjects.

The following will be presented by treatment group and as a total:

- Number and percentage of subjects in each analysis set
- Number and percentage of subjects in each center (using the FAS)
- Number and percentage of subjects in each combination of the stratification factors: age (≥ 65 vs < 65 years) and comorbidities (present vs absent) as recorded at randomization in the IRT system (using the FAS)

The stratification factors as recorded at randomization in the IRT system will be compared to those entered into the clinical database and discrepancies will be summarized.

4.2.2 Protocol deviations

Important protocol deviations are defined in Section 2.2 and will be listed by treatment group and summarized separately by treatment group for all subjects randomized to treatment.

The number and percentage of subjects with any IPD will be summarized for each IPD category. Subjects with more than one deviation in the same IPD category will be counted once for that IPD category. Any subjects who have deviations in more than one IPD category will be counted once in the overall summary.

4.2.3 Demographic and other baseline characteristics

Demographic and other baseline characteristics will be listed for all subjects and summarized by treatment group and overall for the FAS using the rules for summarizing continuous and categorical variables described in Section 4.1.

In addition to being summarized as continuous variables, age, and BMI will be summarized as the following categorical variable: age group (<65 , ≥ 65 years, as well as categories of <20 , ≥ 20 - < 35 , ≥ 35 - < 50 , ≥ 50 - <65 , ≥ 65 - <75 , ≥ 75 years.) and BMI group (Underweight [<18.5], Normal [18.5 - <25.0], Overweight [25.0 - <30.0] and Obese [≥ 30.0]).

The number and percentage of subjects with comorbidities for each treatment group will also be presented, as well as the number of comorbidities (e.g. the number and percentage of subjects in each treatment group with 1, 2, 3, etc. comorbidities) and type.

The number and percentage of subjects with signs and symptoms at screening for each treatment group will be presented overall and by onset time relative to randomization.

The most extreme oxygen treatment or mechanical ventilation received at baseline will also be summarized (most extreme to least extreme: ECMO, invasive ventilation, non-invasive ventilation). If the subject's most extreme treatment is oxygen (no mechanical ventilation was received), maximum oxygen flow rate will be summarized. This will be repeated for prior to baseline, and in addition the duration of any oxygen treatment or mechanical ventilation will be summarized continuously and categorically.

Medical history and surgical history are coded using MedDRA (version 23.0) and will be summarized by System Organ Class (SOC) and Preferred Term (PT).

4.2.4 Prior and concomitant medications and procedures

The following summaries will be produced:

- Summary of prior medications
- Summary of concomitant medications – including best supportive care
- Summary of best supportive care – past
- Summary of best supportive care - current

All concomitant and other treatment data will be listed for all subjects in the FAS.

Missing coding terms should be listed and summarised as "Not coded".

4.3 Analysis of efficacy

The efficacy analyses described in this section are primary or secondary endpoints and will be performed for subjects in the FAS by treatment group (unless stated otherwise).

4.3.1 Primary endpoint

4.3.1.1 Alive and free of respiratory failure at Day 28

The primary endpoint is the proportion of subjects who are alive and free of respiratory failure at Day 28, where respiratory failure is defined in Section 3.1.1.

The point estimate and its 90% confidence interval (CI; using Wald method with continuity correction) will be calculated for each treatment group. The Cochran-Mantel-Haenszel χ^2 test, stratified by age (≥ 65 vs < 65 years) and comorbidities (present vs absent), will be used to compare the proportion of subjects who are alive and free of respiratory failure at Day 28 between the two treatment groups. An unstratified analysis (χ^2 test) will also be performed.

Finally, the difference in the proportion of subjects who are alive and free of respiratory failure at Day 28 will also be provided with 90% CIs. The treatment difference will be also estimated using a logistic regression with indicators for treatment and the randomization stratification factors (2×2) as well as baseline respiratory failure (with vs without).

This primary endpoint will also be summarized (point estimate and 90% CI Wald method with continuity correction as above) by the following subgroups:

- the predefined age categories defined in Section [4.2.3](#)
- sex
- race
- ethnicity
- comorbidities (present vs absent)
- history of substance abuse (former/current/never)
- concomitant antiviral use (yes vs no)
- respiratory failure at baseline (with vs without)

Categories within subgroups may be combined if a category has an insufficient number of subjects, this will be documented in the CSR.

The number and percentage of subjects who experienced respiratory failure but were free of respiratory failure at Day 28 will be summarized by treatment group. This summary will also include summary statistics for the number of respiratory failures that occurred.

All analyses described in this section will be primarily conducted in the FAS but will be repeated for the PPAS.

The proportion for each group, and the difference in proportions, as well as the 90% CIs, will also be reported in the FAS but excluding subjects who have withdrawn or have been lost to follow-up on or prior to Day 14.

The method for handling subjects that withdraw or are lost to follow up on or prior to Day 28 is detailed in Section [3.1.1](#).

Additional sensitivity analyses and subgroup analyses (such as by concomitant medication usage) of the primary endpoint may be performed as appropriate.

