- 12. Uncontrolled or untreated symptomatic arrhythmias, myocardial infarction within the last 6 weeks, or congestive heart failure (NYHA Grade 3 or 4).

Exception: Subjects with controlled, asymptomatic atrial fibrillation during screening are allowed to enroll on study.

13. History of chronic hypercarbia, respiratory failure in past 6 months, or use of home oxygen in the setting of severe chronic respiratory disease.

- 14. Quadriplegia.
- 15. History of primary immunodeficiency, tuberculosis, progressive multifocal leukoencephalopathy (PML), aspergillus or other invasive mold/fungal infection, or received organ or bone marrow transplantation within 6 months of randomization.
- 16. Serology status reflecting active hepatitis B or C infection.
 - a) Subjects who are hepatitis B core antibody (anti-HBc) positive and who are hepatitis B surface antigen (HBsAg) negative will need to have a negative or undetectable hepatitis B viral load by quantitative polymerase chain reaction (PCR) result before randomization. Those who are HBsAg positive or have detectable hepatitis B viral load by PCR will be excluded.
 - b) Subjects who are hepatitis C virus (HCV) antibody positive will need to have a negative PCR result before randomization. Those who are hepatitis C PCR positive will be excluded.
- 17. Known active HIV with detectable viral load or CD4 counts < 500 cells/mm³.

Prior/Concomitant Therapy

- 18. Treatment with a strong cytochrome P450 (CYP)3A inhibitor (within 7 days before first dose of study drug) or inducer (within 14 days before first dose of study drug).
- Subjects are excluded who have already received prior immunomodulatory/ immunosuppressive treatment intended as specific treatment for COVID-19 (after randomization these agents may be permitted – see Section 6.5.2). Note: Steroids are permitted prior to randomization and on study..
- 20. Active participation in other drug clinical trials or received treatment with an investigational drug within 5 half-lives or 30 days (whichever is longer) of randomization/enrollment.

Exception: Subjects may receive COVID-19-specific antiviral drugs (eg, remdesivir, hydroxychloroquine).

- 21. Requires or is receiving specific anticoagulation with warfarin or equivalent vitamin K antagonists (eg, phenprocoumon) within 7 days prior to randomization. Other anticoagulants are permitted.

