1.3 Number of subjects

The planned total number of subjects in this study is approximately 60. Sixty (60) subjects meeting the eligibility criteria will be randomized in a 1:1 ratio to either Arm 1 (acalabrutinib plus BSC; n=30) or Arm 2 (BSC; n=30).

It is assumed that the proportion of subjects who are alive and free of respiratory failure at Day 14 is 70% under BSC. A targeted difference of 20% between two treatment arms (i.e., 90% for acalabrutinib + BSC) is of clinical interest. With a total sample size of 60, the half-width of the 2-sided 90% confidence interval for the observed treatment difference is 16.4% using unpooled estimate for variance. It has approximately 64% power, with a 2-sided type I error of 0.1, to detect a difference of 20% between the 2 arms.

At the time that the SAP version 3.0 was generated (amendment of version 2.0), the study recruitment was complete with a total of 62 subjects randomized.

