3.5.2 Prior and concomitant medications and procedures

All therapies (drug and non-drug), including herbal preparations, whether prescribed or over-the-counter, that are used during the study will be recorded on the eCRF. Details include generic and/or brand names of the medications, World Health Organisation Drug Dictionary (WHO-DD) encoding (B3 format), reason for use, route, dose, dosing frequency, and start and end dates. Procedures performed during the study will be recorded on the eCRF and details include the procedure name, WHO-DD encoding (B3 format), reason for the procedure, and start and end dates.

Prior therapies are defined as those taken prior to study treatment with a stop date prior to the first dose of study treatment (acalabrutinib + BSC subjects) or prior to randomization (BSC only subjects). For subjects on acalabrutinib + BSC, concomitant therapies and procedures are defined as those with a stop date on or after the first dose date of study treatment. Start date may be before or after first dose. For subjects on BSC only, concomitant therapies and procedures are defined as those with a stop date on or after randomization. Start date may be before or after randomization.

Best supportive care medication will be collected as a concomitant medication with therapy reason as 'disease under study'.

Missing start and stop dates for medications and procedures will be handled using the rules described in Section 4.1

Medications received prior to or concomitantly will be coded using the WHO Drug Dictionary Anatomical Therapeutic Chemical (ATC) classification codes. Concomitant medications will be summarized for the FAS by ATC classification codes. Subjects with the same concomitant medication/procedure multiple times will be counted once per medication/procedure. A medication/procedure that can be classified into more than one chemical and/or therapeutic subgroup will be presented in each subgroup.

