No imputation of values for missing data will be performed except for missing or partial start and end dates for AEs and concomitant medication(CM) (Table 6). If the data cut-off/snapshot date or the subject’s date of death is prior to the date imputed based on the rules outlined below, then the earliest of these dates will be imputed.

Table 6 Imputation rules for missing or partial AE on concomitant medication dates

Form		Imputation	
		Acalabrutinib + BSC	BSC alone
	Start date		
	Missing		

AE and CM	AE/CM ended before first dose date/ randomization date	Impute 1 st January with year being the same year as CM/AE end date	
	AE/CM ended after first dose date/ randomization date	Impute date of first dose	Impute date of randomization
	Partial		
AE and CM	Missing day	Impute 1 st of the month unless AE/CM start month is the same month as the first dose, then impute date of first dose. Check start date is prior to end date.	Impute 1 st of the month unless AE/CM start month is the same month as randomization, then impute date of randomization. Check start date is prior to end date.
	Missing day and month	Impute 1 st January unless AE/CM start year is the same year as the first dose, then impute date of first dose. Check start date is prior to end date. If end date is now prior to start date, impute 1 st January as the start day and month.	Impute 1 st January unless AE/CM start year is the same year as randomization, then impute date of randomization. Check start date is prior to end date. If end date is now prior to start date, impute 1 st January as the start day and month.
	End date		
	Missing		
AE and CM	CM flag ongoing takes any value (yes, no or missing) and CM start date is prior, on or after first dose date/ randomization AE stop date missing	Impute min (date of death, data cut-off/snapshot date)	
	Partial		
CM	Missing day	Impute the last day of the month unless month is the same as month of last dose, then impute date of last dose.	Impute the last day of the month unless month is the same as month of randomization date + 10 days, then impute randomization date + 10 days.

	Missing day and month	Impute date of last dose + 28 days + 3 days	Impute date of randomization + 38 days + 3 days
--	-----------------------	---	---

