4.3.2 Secondary endpoints

4.3.2.1 Alive and free of respiratory failure at Day 14

The point estimate and its 90% confidence interval (CI; using Wald method with continuity correction) will be calculated for each treatment group. Summaries of the subgroups specified in Section 4.3.1.1 will also be produced. Analyses may be repeated for the PPAS, using the definition of the PPAS in Section 3.1.2.

The proportion for each group, and the difference in proportions, as well as the 90% CIs, will also be reported in the FAS but excluding subjects who have withdrawn or have been lost to follow-up on or prior to Day 28.

The number and percentage of subjects who experienced respiratory failure but were free of respiratory failure at Day 14 will be summarized by treatment group. This summary will also include summary statistics for the number of respiratory failures that occurred.

The method for handling subjects that withdraw or are lost to follow up on or prior to Day 14 is detailed in Section 3.1.2.

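### Subgroup tables for the primary endpoint use a Wald interval that can under-cover badly in small, high-success cells, and the antiviral subgroup can count treatment started after randomization

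*SAP*

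**What the plan says.** SAP 4.3.1.1 gives each arm's proportion alive and free of respiratory failure at Day 28 with a 90% Wald interval with continuity correction. It then says "This primary endpoint will also be summarized (point estimate and 90% CI Wald method with continuity correction as above) by the following subgroups", and lists eight factors. One is the set of age categories in SAP 4.2.3, which includes six bands as well as the split at 65 years. SAP 4.3.2.1 repeats this for Day 14: "Summaries of the subgroups specified in Section 4.3.1.1 will also be produced".

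The provision for sparse cells is "Categories within subgroups may be combined if a category has an insufficient number of subjects, this will be documented in the CSR". No minimum size is given. SAP 1.3 records that "the study recruitment was complete with a total of 62 subjects randomized".

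Another factor is "concomitant antiviral use (yes vs no"), which the subgroup list in Protocol 9.6.2 does not name. SAP 3.5.2 defines concomitant therapy by stop date. For BSC-only subjects, "concomitant therapies and procedures are defined as those with a stop date on or after randomization. Start date may be before or after randomization"; for the acalabrutinib arm the anchor is first dose instead of randomization. Antivirals are allowed around entry (Protocol 5.2, criterion 20 exception: "Subjects may receive COVID-19-specific antiviral drugs"), and Protocol 6.5.2 permits remdesivir as part of BSC where local authorities recommend it and institutional guidelines include it.

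**The concern.** The Wald standard error is computed from the observed proportion, so it vanishes when all subjects succeed. Only the continuity term 1/(2n) is then left. The cells with the least information can therefore show the narrowest intervals, mostly where success is high, which is where a reader looks for benefit. The study estimates effects and plans no formal hypothesis test (Protocol 9.1), so readers will rely on the intervals.

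The antiviral factor raises a different problem. A subgroup that depends on what happens after randomization can be affected by the assigned arm and by the clinical course. Site staff know the assignment. If deteriorating patients are given antivirals more often in one arm, the split sorts failures unevenly between the yes and no rows, and a contrast appears that the drug did not cause. SAP 3.5.2 also sets no upper limit on the start date, so, read literally, an antiviral begun after Day 14 could classify a Day 14 outcome.

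**Working it through.** **Inputs.** Planning rates of 70% (BSC) and 90% (acalabrutinib + BSC), Protocol 9.2. Randomized: 62, about 31 per arm, SAP 1.3. Level 90%, z = 1.645. The documents give no expected cell sizes. If subjects were spread evenly (assumption), 31 per arm gives about 5 per cell for six age bands, 10 for three levels and 15 for two.

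**The plan's own figures.** Half-width for the difference with 30 per arm: 1.645 × √(0.7×0.3/30 + 0.9×0.1/30) = 1.645 × 0.100 = 16.4 points, as stated. Power with unpooled variance: Φ(0.20/0.100 − 1.645) = 63.9%, which agrees with the stated 64%.

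**Interval.** For x successes out of n, with p̂ = x/n, the limits are p̂ ± [1.645 × √(p̂(1−p̂)/n) + 1/(2n)]. If x = n this becomes 1 ± 1/(2n):

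- 5 of 5: 90% to 110%
- 10 of 10: 95% to 105%. For the same data Wilson gives 78.7% to 100% and Clopper-Pearson 74.1% to 100%.

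**Exact coverage.** For each n and true rate p, sum the binomial probabilities of all x whose interval contains p. Example: n = 10, p = 0.90. The interval contains 0.90 only for x = 6 to 9. The all-success result alone, with probability 0.9^10 = 34.9%, misses, and coverage is 65.0%.

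| n | Wald, p = 0.90 | Wilson, p = 0.90 | Clopper-Pearson, p = 0.90 | Wald, p = 0.70 |
|---|---|---|---|---|
| 5 | 99.1% | 91.9% | 99.1% | 80.1% |
| 6 | 46.7% | 88.6% | 98.4% | 87.1% |
| 8 | 56.5% | 96.2% | 96.2% | 93.1% |
| 10 | 65.0% | 93.0% | 98.7% | 96.1% |
| 15 | 79.2% | 94.4% | 98.7% | 94.9% |
| 31 | 95.2% | 87.8% | 93.1% | 91.3% |

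(Wald here means with continuity correction.) The 99.1% at n = 5 arises only because the 5-of-5 lower limit is exactly 90%; at n = 6 it moves to 91.7% and misses, and 6 of 6 occurs with probability 0.9^6 = 53.1%. Over n = 5 to 15 at both planning rates, Wilson covers 86.1% to 97.4% and Clopper-Pearson 92.1% to 99.2%. At p = 0.90 the untruncated Wald upper limit passes 100% with probability 93.0% (n = 10) and 94.4% (n = 15).

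**Antiviral split with no treatment effect.** All rates here are assumptions. Let 30% fail in both arms, let b be the share on antivirals at baseline, and let only failing patients start later, at rate r among those not already treated. Then:

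- success in the yes row = 0.7b / [0.7b + 0.3(b + (1−b)r)]
- success in the no row = 0.7 / [0.7 + 0.3(1−r)], where b cancels

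With b = 0.3:

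- r = 0.2: yes 0.21/0.342 = 61.4%, no 0.49/0.658 = 74.5%
- r = 0.3: yes 0.21/0.363 = 57.9%, no 0.49/0.637 = 76.9%
- r = 0.5: yes 0.21/0.405 = 51.9%, no 0.49/0.595 = 82.4%

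Differences, acalabrutinib minus BSC, from unrounded values:

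| Start rate, BSC vs acalabrutinib | Yes row | No row |
|---|---|---|
| 50% vs 20% | +9.6 | −7.9 |
| 30% vs 20% | +3.6 | −2.5 |
| equal | 0 | 0 |

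With b = 0.7 the yes-row figures fall to +2.5 and +0.8, and the no-row figures are unchanged.

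**The case against.** The case for leaving this alone has substance. These are descriptive tables with no interaction test or decision rule. The worst coverage needs a true rate near 90% and cells of about 6 to 15; at 70%, coverage for n = 6 to 15 is 86.5% to 96.1%. Cell sizes are assumed. Wilson also dips below nominal (84.6% at p = 0.80, n = 13). The SAP does not say that limits above 100% will be printed, and truncating them is a display choice. The Wald method was adopted in Amendment 1 after regulator feedback, and the log does not confine it to the arm level. On antivirals, the start rates are invented, and patients who fail, start an antiviral and recover by Day 28 count as successes, which shrinks the artefact. In the +9.6 scenario the yes cells hold about 31 × 0.342 = 11 and 31 × 0.405 = 13 subjects, so the 90% half-width of that difference is about ±34 points.

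Most of this stands as a limit on importance, but it does not remove either defect. Truncation leaves the collapsed lower limit in all-success cells untouched. Pooling is optional, has no threshold, and for a two-level factor removes the subgroup altogether. Wilson's dips are a few points, against more than 40 for the Wald interval at n = 6. Labelling the factor as concomitant discloses the definition but does not make it a baseline factor.

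**Conclusion.** Both parts hold. At the plan's own target rate of 90%, the subgroup interval covers 46.7% to 79.2% for cells of 6 to 15 instead of 90%. Coverage is erratic rather than uniformly low, and the range of cell sizes is an assumption. The arm-level interval is acceptable at the planning rates (91.3% and 95.2% at n = 31). The antiviral subgroup is partly a post-randomization variable by the SAP's own definition. The size of any resulting bias cannot be known from the documents; the assumed scenarios run from zero to just under 10 points. The primary conclusion is not affected. What is at risk is how the subgroup tables are read, and since the correction is cheap it should be made.

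**What to change.** 1. In SAP 4.3.1.1 and 4.3.2.1, use Wilson or Clopper-Pearson 90% intervals for the subgroup summaries. Clopper-Pearson is the conservative choice; Wilson is narrower but can fall a few points below nominal. Keep the continuity-corrected Wald interval for the arm-level result and footnote the difference.
2. Define the antiviral subgroup as antiviral started before randomization (yes vs no), with randomization as the anchor in both arms.
3. State one rule, the same in both arms, for same-day starts and for missing or partial start dates. This is needed because SAP Table 6 imputes a start date with a missing day, for BSC alone, as the first of the month "unless AE/CM start month is the same month as randomization, then impute date of randomization", and to first dose in the acalabrutinib arm. Under the new definition that would class a true baseline antiviral as not started before randomization. The rule should also say how courses that ended before randomization are classed, since SAP 3.5.2 treats those as prior therapy.

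The cost is three SAP sentences and a table footnote. Start dates are already collected, though a few may need a query. The downside is that overall and subgroup intervals for the same endpoint will use different methods.

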2.1.2 Per-protocol analysis set

The per-protocol analysis set (PPAS) will be a subset of the ITT population including only subjects without important detected protocol deviations affecting the efficacy endpoints. Subjects will be summarized according to the actual treatment received. The primary efficacy endpoint of the study will also be summarized for this population.

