3. PRIMARY AND SECONDARY VARIABLES

3.1 Efficacy variables

3.1.1 Alive and free of respiratory failure at Day 28

The primary endpoint is the proportion of subjects who are alive and free of respiratory failure at Day 28. For the purpose of this study respiratory failure is defined based on resource utilization of any of the following modalities:

- Endotracheal intubation and mechanical ventilation;
- Oxygen delivered by high-flow nasal cannula (heated, humidified, oxygen delivered via reinforced nasal cannula at flow rates >20L/min with fraction of delivered oxygen ≥50%);
- Non-invasive positive pressure ventilation or continuous positive airway pressure;
- Extracorporeal membrane oxygenation.

Only the subject's survival status and respiratory-failure status on Day 28 will be considered for this endpoint. No visit window will be used for this endpoint. If they experience respiratory failure after randomization but recover by Day 28, per the definition above, they will be considered alive and free of respiratory failure at Day 28.

For the FAS analysis, subjects who withdraw or are lost to follow up on or prior to Day 28, thus survival status and respiratory status at Day 28 cannot be assessed, will be included in the denominator of this analysis as though they had died or had a respiratory failure.

For the PPAS analysis, subjects who withdraw or are lost to follow up on or prior to Day 28, thus survival status and respiratory status at Day 28 cannot be assessed, will be excluded from this analysis, hence the percentage for each treatment group will be calculated as:

$$\frac{\text{Number of subjects alive and free of respiratory failure at Day 28}}{\text{Number of subjects who have died or are still in the study at Day 28}} \times 100\%$$

To avoid a biased estimate of the proportion for DMC review, the subjects included in this analysis (based on the FAS and PPAS definitions) will be restricted to subjects who reached Day 28 (or would have reached Day 28 had they not died, withdrawn or been lost to follow up) at the time the analysis. This will be considered the full analysis set evaluable at Day 28.

3.1.2 Alive and free of respiratory failure at Day 14

This is defined as the proportion of subjects who are alive and free of respiratory failure at Day 14. Respiratory failure is defined the same as specified in Section 3.1.1 above.

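### The FAS re-analyses that exclude lost subjects use crossed cut-off days: Day 14 for the Day 28 endpoint and Day 28 for the Day 14 endpoint

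*SAP*

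**What the plan says.** **Handling rules.** SAP 3.1.1 (Day 28 endpoint) takes FAS subjects who withdraw or are lost on or before Day 28 and cannot be assessed, and says that they "will be included in the denominator of this analysis as though they had died or had a respiratory failure". SAP 3.1.2 applies the same treatment to the Day 14 endpoint with a Day 14 limit. Its FAS rule names only subjects lost to follow-up, not those who withdraw.

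**Day 28 analysis, SAP 4.3.1.1.** The group proportions, their difference and 90% CIs are also to be reported in the FAS "excluding subjects who have withdrawn or have been lost to follow-up on or prior to Day 14". The next sentence of the section, "The method for handling subjects that withdraw or are lost to follow up on or prior to Day 28", refers back to 3.1.1 and uses Day 28.

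**Day 14 analysis, SAP 4.3.2.1.** The parallel re-analysis is done "excluding subjects who have withdrawn or have been lost to follow-up on or prior to Day 28". The section's closing sentence, "The method for handling subjects that withdraw or are lost to follow up on or prior to Day 14", refers back to 3.1.2 and uses Day 14.

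**Per-protocol analysis set (PPAS).** The Day 28 rule in 3.1.1 uses the matching day: "For the PPAS analysis, subjects who withdraw or are lost to follow up on or prior to Day 28" are left out. SAP 2.1.2 adds that "Subjects will be summarized according to the actual treatment received". The primary analyses will be repeated in the PPAS. For Day 14 the repeat is optional: "Analyses may be repeated for the PPAS, using the definition of the PPAS in Section 3.1.2".

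**The concern.** Each section uses one day for its handling rule and the other day for its re-analysis, and the two sections mirror each other. No reason is given, so this looks like an exchange of two numbers and not a design decision.

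The SAP does not say what the re-analyses are for. The natural reading is that they show the FAS result once the imputed failures are taken out. With crossed days they do that only if nobody is lost on Days 15-28. Otherwise the Day 28 check keeps some imputed failures, and can suggest that the result is insensitive to the missing-as-failure rule when it is not. The Day 14 check, in turn, selects subjects on follow-up after the endpoint day.

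**Working it through.** **Inputs.** From protocol 9.2 and SAP 1.3: 30 per arm, 90% on acalabrutinib plus BSC against 70% on BSC, two-sided 90% interval. As counts, this is 27/30 against 21/30. The number, arm and timing of losses are assumptions, because the documents give none. Lost subjects are taken to be among the non-successes at Day 28, as the FAS rule requires.

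**The plan's own figures.** Half-width = 1.645 × √(0.9×0.1/30 + 0.7×0.3/30) = 1.645 × 0.100 = 16.4 points, as stated. Power with unpooled variance = Φ(0.20/0.100 − 1.645) = 63.9%, stated as about 64%. Both reproduce.

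**Who is excluded.** Let E be subjects lost by Day 14 and L those lost on Days 15-28.

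| Endpoint | Imputed as failure (3.1.1, 3.1.2) | Removed as written | Consequence |
|---|---|---|---|
| Day 28 | E and L | E only | L stay in as imputed failures |
| Day 14 | E only | E and L | L dropped although Day 14 status could be observed |

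If L is empty, the written and matched versions coincide.

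**Day 28 check, all losses on Days 15-28.** Interval = difference ± 1.645 × √(p1(1−p1)/n1 + p2(1−p2)/n2), without continuity correction. As written, nobody is removed, so every row stays at 27/30 − 21/30 = 20.0 (3.6 to 36.4).

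| Assumed late losses | Matched check, points (90% CI) | Gap from 20.0 |
|---|---|---|
| 1 BSC | 27/30 − 21/29 = 17.6 (1.2 to 33.9) | 2.4 |
| 2 BSC | 27/30 − 21/28 = 15.0 (−1.2 to 31.2) | 5.0 |
| 3 BSC | 27/30 − 21/27 = 12.2 (−3.7 to 28.2) | 7.8 |
| 1 acalabrutinib | 27/29 − 21/30 = 23.1 (7.3 to 38.9) | 3.1 |
| 2 acalabrutinib | 27/28 − 21/30 = 26.4 (11.5 to 41.4) | 6.4 |

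**Day 28 check, two losses in each arm.** Matched: 27/28 − 21/28 = 21.4.

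- Acalabrutinib losses by Day 14 and BSC losses late: as written 27/28 − 21/30 = 26.4, an overshoot.
- Timing reversed: as written 27/30 − 21/28 = 15.0. This moves down from 20.0 when the matched value moves up.

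**Day 14 check, nobody lost by Day 14 and three BSC subjects lost on Days 15-28.** The same 27/30 and 21/30 stand in for the Day 14 results. Matched: 20.0, since nothing is imputed. As written:

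- all three were Day 14 successes: 27/30 − 18/27 = 23.3;
- all three were Day 14 failures: 27/30 − 21/27 = 12.2.

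**The case against.** The strongest reply is that little depends on these tables. They are supplementary, carry no test, and are not required by the protocol, which asks for FAS and PPAS analyses and leaves further sensitivity analyses optional. The adjacent references to the handling rules give the matching day, so a careful programmer might query the text. This limits the severity, but the instruction is still wrong as written.

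For the primary endpoint, the PPAS repeat is mandatory and uses the matching day. The deviation list in SAP 2.2 is short (never dosed, four eligibility criteria, pregnancy without withdrawal from treatment), so with few deviators the PPAS may come close to the intended check. It still removes those deviators and groups by actual treatment, so it does not isolate the rule in the FAS. The Day 14 repeat is only optional.

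The magnitudes are illustrations, some of them extreme. Three of 30 BSC subjects lost in two weeks is 10%. The two-arm cases need opposite timing by arm. The 12.2 end of the Day 14 range needs three subjects in respiratory failure on Day 14 who were later lost and not known to have died. The SAP names the continuity-corrected Wald method for the single-arm intervals but no method for the difference. With a standard correction of ½(1/30 + 1/30) = 3.3 points, the lower limit as written falls from 3.6 to about 0.2. For two late BSC losses, the matched limit stays below zero.

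The purpose of the re-analyses is inferred. That is a fair caveat, but no other purpose is documented that would explain the crossed days.

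**Conclusion.** The concern holds. The text in 4.3.1.1 and 4.3.2.1 contradicts the handling rules and the matching-day references in the same sections. The consequence depends on whether anyone is lost on Days 15-28: with no such loss the gap is zero. With one to three such losses in a single arm at the planning rates, the Day 28 check is off by about 2 to 8 points, in either direction. With losses in both arms it can overshoot or move the wrong way. These sizes rest on assumed loss counts and on 30 per arm; SAP 1.3 reports 62 randomized in all. The main FAS estimate, the tests, the sample size and the power are unaffected. It should be corrected, but it does not threaten the primary analysis.

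**What to change.** In SAP 4.3.1.1, change the day in the exclusion sentence from 14 to 28. In SAP 4.3.2.1, change it from 28 to 14. In SAP 3.1.2, extend the FAS rule, and the PPAS sentence for consistency, to subjects who withdraw as well as those lost to follow-up, as 3.1.1 already does.

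Two separate wording slips, which add no weight to this point, can be corrected at the same time. SAP 3.1.7 (alive and discharged from the ICU) carries respiratory-failure wording in its FAS rule, PPAS sentence and PPAS numerator, where ICU status is meant. SAP 1.3 places the 70% planning rate at Day 14, where protocol 9.2 gives Day 28.

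The cost is SAP wording only, with no new data and no extra table. The change should be made before database lock, so that the check remains prespecified and does not appear to respond to the observed losses.
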